| Study Day or Week ^b | N/A | N/A | Day -14 | Day 1 ^c | Wk 6 | Wk 12 | Wk 18 | Wk 26 | Wk 30 | Wk 39 | Wk 52 | Wk 65 | Wk 78 | Wk 91 | Wk 104 or ET ^d | 2 Wk f/u phone call ^e | Rescue Visit ^f |
| Visit Window | | | | ±5 days | ±7 days | ±7 days | ±7 days | ±7 days | ±7 days | ±14 days | ±14 days | ±14 days | ±14 days | ±14 days | ±14 days | ±3 days | |
| Assess Compliance | | | | X | X | X | X | X | | X | X | X | X | X | X | | X |
| Prior/Concomitant medication review | X | X | X | X | X | X | X | X | X | X | X | X | X | X | X | | |
| Subject Education / Monitoring | | | | | | | | | | | | | | | | | |
| Diet and Exercise Counseling (S2)/Monitoring ^w | | X | X | X | X | X | X | X | | X | X | X | X | X | X | | X |
| Distribute glucose meter (S2) and glucose meter supplies | | X | X | X | X | X | X | X | | X | X | X | X | X | | | X |
| Dispense Hypoglycemia Assessment and Self-Monitoring Blood Glucose logs and instruct on hypoglycemia (symptoms and management) and hyperglycemia symptoms ^x | | X | | | | | | | | | | | | | | | |
| Review/dispense Hypoglycemia Assessment and Self-Monitoring Blood Glucose logs | | | X | X | X | X | X | X | X | X | X | X | X | X | X | | X |
| Adverse Event Monitoring ^y | | X | X | X | X | X | X | X | X | X | X | X | X | X | X | X | X |

- A separate S2 visit is required for subjects taking metformin monotherapy for less than 8 weeks at the S1 visit and for those who require a change to their diabetes regimen at the S2 visit (including subjects who require discontinuation of their AHA therapy at the S2 visit). These subjects must remain on metformin monotherapy ≥1500 mg/day for at least 8 weeks prior to repeating the HbA1c at S3 for determination of eligibility. Subjects whose HbA1c at S1 is ≥7.0 and ≤10.5% and are on metformin monotherapy ≥1500 mg/day for at least 8 weeks at S1, will have a combined S2/S3 visit.
- Day 1 has a recommended visit window of ±5 days relative to S3 (or combined S2/S3 visit); Weeks 6, 12, 18, 26, 30 have a recommended visit window of ±7 days relative to Day 1; Visits from Week 39 through 104 have a recommended visit window of ±14 days relative to Day 1; 2 week follow-up phone call is recommended to be completed within a ±3-day window.

- c. All Day 1 procedures to be completed prior to dosing.

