- d. ET = Early termination, subjects who discontinue taking investigational product prematurely should complete procedures for the ET visit and have a 2-week follow-up phone call from their last dose of investigational product. In addition, if subjects agree, they will also be contacted via telephone by the Investigator/qualified designee according to the same schedule as if the subjects were still taking investigational product to assess for SAEs and to collect information on clinical events per [Section 7.8](#), if applicable. See [Section 6.7](#) for additional details.
- e. Each randomized subject should have a follow-up phone call 14 ±3 days after the last dose of investigational product to assess for SAEs and to collect information on clinical events per [Section 7.8](#), if applicable.
- f. Subjects who require glycemic rescue therapy per [Section 5.6](#) must have rescue therapy initiated at either a scheduled or unscheduled visit, and not by a telephone call.
- g. Brief physical examination includes assessment of heart, lungs, abdomen, extremities and skin.
- h. Sitting triplicate blood pressure and pulse rate should be collected, as instructed in [Section 7.4.2](#).
- i. Duplicate measurements of supine and standing blood pressure and pulse rate should be taken per [Section 7.4.3](#). Postural changes should only be collected at the Rescue Visit if the Rescue Visit occurs in Phase A.
- j. S2 ECG is read locally at investigative site. ECG for all other time points should be submitted to be read centrally.
- k. Screening DXA scans should be performed at Visit S3 or at least ten days before Day 1 visit. In case of discontinuation of investigational product during Phase A, a DXA scan will be performed if the discontinuation occurs between Week 12 and Week 26. In case of discontinuation of investigational product during Phase B, a DXA scan will be performed if the discontinuation occurs at least 12 weeks from the previous scan. See [Section 7.6](#) for additional details.
- l. Routinely collected urinalysis samples will be sent to the central laboratory for dipstick analysis (not including glucose assessment) and microscopy if dipstick is positive for blood, nitrites, leukocytes and/or protein.

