- u. The Future Biomedical Research (FBR) informed consent must be obtained before FBR samples are drawn. The FBR sample for DNA analysis should be obtained pre-dose, at Day 1/Visit 4, as the last sample drawn, on subjects who qualify for randomization, but may be obtained at a later date during the trial after the FBR informed consent is obtained. The plasma and serum samples for FBR should be collected at Day 1 (pre-dose), Week 26, Week 104 or Early Termination Visit, and Rescue Visit (if applicable). The plasma and serum samples for FBR should be collected at all time points, even if the pre-dose or other time point was not collected.
- v. The sample(s) for measurement of bone biomarkers and PTH should not be collected if the investigational product has been discontinued for >7 days prior to the collection of the sample(s).
- w. Subjects will be seen by a dietician or qualified healthcare professional for dietary and exercise counseling at S2 Visit only; at other visits subjects should be asked about their diet and exercise which may be done by other appropriate site personnel evaluating the subject.
- x. Subjects should be educated on the symptoms of hyperglycemia (eg, polyuria, polydipsia) at S2.
- y. Assess AEs, SAEs, hypoglycemia assessment log as well as potential clinical events for adjudication (See [Sections 7.4.6, 7.8, 8](#) for additional detail).

TABLE OF CONTENTS

| | |
|--|----|
| LIST OF TABLES | 24 |
| LIST OF FIGURES | 24 |
| APPENDICES | 25 |
| 1. INTRODUCTION | 30 |
| 1.1. Indication..... | 30 |
| 1.2. Background | 30 |
| 1.3. Efficacy of Ertugliflozin..... | 31 |
| 1.4. Safety Information for Ertugliflozin and Other SGLT2 Inhibitors | 31 |
| 1.5. Rationale for Study and Design | 33 |
| 1.5.1. Rationale for Dose Selection of Ertugliflozin | 34 |
| 1.5.2. Rationale for Future Biomedical Research..... | 35 |
| 2. STUDY OBJECTIVES, HYPOTHESES AND ENDPOINTS | 35 |
| 2.1. Objectives and Hypotheses | 35 |
| 2.2. Endpoints..... | 38 |
| 2.2.1. Primary Endpoint..... | 38 |
| 2.2.2. Secondary Endpoints | 38 |
| 3. STUDY DESIGN..... | 39 |
| 4. SUBJECT SELECTION..... | 43 |
| 4.1. Inclusion Criteria..... | 43 |
| 4.2. Exclusion Criteria..... | 45 |
| 4.3. Randomization Criteria | 50 |
| 4.4. Life Style Guidelines..... | 51 |
| 4.4.1. Dietary Restrictions | 51 |
| 4.4.2. Physical Activities | 51 |
| 4.4.3. Alcohol, Caffeine and Tobacco | 51 |
| 4.4.4. Female Contraception..... | 52 |
| 4.4.4.1. Females– Non-childbearing Potential | 52 |

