6.5. Follow-up Phone Call

Each randomized subject should have a follow-up phone call 14 days after the last dose of investigational product to assess for AEs, SAEs and collect information on clinical events per [Section 7.8](#), if applicable. The phone call should be completed within a ± 3 day window.

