8. ADVERSE EVENT REPORTING

8.1. Assessing and Recording Adverse Events

An adverse event is defined as any untoward medical occurrence in a patient or clinical investigation subject administered a pharmaceutical product and which does not necessarily have to have a causal relationship with this treatment. An adverse event can therefore be any unfavourable and unintended sign (including an abnormal laboratory finding, for example), symptom, or disease temporally associated with the use of a medicinal product or protocol-specified procedure, whether or not considered related to the medicinal product or protocol-specified procedure. Any worsening (ie, any clinically significant adverse change in frequency and/or intensity) of a preexisting condition that is temporally associated with the use of the Sponsor's product, is also an adverse event.

Changes resulting from normal growth and development that do not vary significantly in frequency or severity from expected levels are not to be considered adverse events. Examples of this may include, but are not limited to, teething, typical crying in infants and children and onset of menses or menopause occurring at a physiologically appropriate time.

Sponsor's product includes any pharmaceutical product, biological product, device, diagnostic agent or protocol-specified procedure, whether investigational (including placebo or active comparator medication) or marketed, manufactured by, licensed by, provided by or distributed by the Sponsor for human use.

Adverse events may occur during the course of the use of the Sponsor's product in clinical trials or within the follow-up period specified by the protocol, or prescribed in clinical practice, from overdose (whether accidental or intentional), from abuse and from withdrawal.

Adverse events may also occur in screened subjects during any pre-allocation baseline period as a result of a protocol-specified intervention, including washout or discontinuation of usual therapy, diet, placebo treatment or a procedure.

All adverse events will be recorded from the time the consent form is signed through 14 days following cessation of treatment and at each examination on the Adverse Event case report forms/worksheets.

090177e1848ce2dd\Approved\Approved On: 23-Sep-2013 15:48

8.2. Definition of an Overdose for This Protocol and Reporting of Overdose to the Sponsor

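### The follow-up call may be made from Day 11 although adverse events are to be recorded through Day 14, and footnote e conflicts with Section 6.5 on whether non-serious events are asked about

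*Combined protocol and SAP*

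**What the plan says.** **Recording period.** Section 8.1 states: "All adverse events will be recorded from the time the consent form is signed through 14 days following cessation of treatment". Section 8.4.1 gives the same limit for SAEs. It adds that an SAE judged related must be reported whenever it comes to the investigator's attention. Section 7.8.1 collects cardiovascular events to the end of the study, including a 14-day post-dose period.

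**Timing of the call.** The Schedule's window row, footnotes b and e, and Section 6.5 all give Day 14 with a tolerance of 3 days either way. Footnote b calls this window recommended, and Section 6 says that visit windows generally are recommended, not required.

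**Content of the call.** Footnote e describes a "follow-up phone call 14 ±3 days after the last dose of investigational product to assess for SAEs and to collect information on clinical events". Section 6.5 describes the same contact as a "follow-up phone call 14 days after the last dose of investigational product to assess for AEs, SAEs and collect information on clinical events". In the Schedule, the row "Adverse Event Monitoring ^y" is marked in the column for the 2-week call, and footnote y to that row reads "Assess AEs, SAEs, hypoglycemia assessment log as well as potential clinical events for adjudication".

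**Early stoppers.** Footnote d says that subjects who stop investigational product prematurely should complete the early termination procedures and "have a 2-week follow-up phone call from their last dose of investigational product". It says nothing about the content of that call. It then adds that subjects who agree will also be telephoned "according to the same schedule as if the subjects were still taking investigational product to assess for SAEs" and Section 7.8 events. Section 6.7.2 repeats the telephone schedule and asks these subjects back at Week 104.

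**The concern.** A recording period is only as complete as the last contact that asks about it. If that contact may come before the period ends, anything on the remaining days is found only if the subject volunteers it. For a subject who completes Week 104, no further contact is scheduled after the follow-up call.

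The second difficulty is that two notes to the same Schedule describe the same call differently. Footnote e belongs to the call's own column and names SAEs and Section 7.8 events. Footnote y belongs to a row marked in that column and names AEs too. Site staff working from the column note alone could leave non-serious events unasked. The Tier-1 events in Section 9.3 (urinary tract infection, genital mycotic infection, hypoglycemia, hypovolemia) need not be serious, so they are the kind of event that such a reading would miss.

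What is at stake is the completeness and consistency across sites of post-treatment safety data. No efficacy result is involved.

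**Working it through.** **Step 1. Inputs.** The recording period is 14 days after the last dose (Sections 8.1 and 8.4.1). The call target is Day 14 and the tolerance is 3 days either way (footnotes b and e, Section 6.5). Treatment lasts 104 weeks for a completer.

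**Step 2. Days left after the call.**
- Earliest in-window call: 14 − 3 = Day 11. Latest: 14 + 3 = Day 17.
- After a Day 11 call, Days 12, 13 and 14 remain: 3/14 = 21% of the period.
- After a Day 12 call, 2 days remain; after a Day 13 call, 1; from Day 14 on, none.

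**Step 3. Average loss.** The documents do not say how calls will be distributed, so this needs an assumption. The possible range for in-window calls is 0 days (every call on Day 14 or later) to 3 days (every call on Day 11). If calls are spread evenly over the seven days 11 to 17, then 3 in 7 come before Day 14. The mean loss is (3 + 2 + 1 + 0 + 0 + 0 + 0)/7 = 6/7 = 0.86 day, and 0.86/14 = 6%.

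**Step 4. Against total observation.** A completer is observed for 104 × 7 + 14 = 742 days, and 3/742 = 0.4%. For a subject who stops at Week 6, treatment plus recording period is 42 + 14 = 56 days, and 3/56 = 5%. The second figure concerns non-serious AEs, or subjects who decline further contact; Step 5 explains why.

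**Step 5. Who has a later contact.**

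| Subject | Scheduled contact after the 2-week call | What it covers |
|---|---|---|
| Completes Week 104 | None | – |
| Stops early and agrees to follow-up | Telephone contacts on the original visit schedule; asked back at Week 104 | Telephone contacts: SAEs and Section 7.8 events (footnote d) |
| Stops early and declines contact | None | – |

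For the middle group, SAEs and adjudicated events on Days 12 to 14 can still be picked up. Non-serious AEs are not part of the telephone contacts. A subject who returns at Week 104 may be asked about AEs then, possibly long after the event.

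**Step 6. What the call asks.**

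| Source | AEs named? | SAEs named? | Section 7.8 or adjudicated events named? |
|---|---|---|---|
| Footnote e | No | Yes | Yes |
| Section 6.5 | Yes | Yes | Yes |
| AE monitoring row, marked at the call, with footnote y | Yes | Yes | Yes |
| Footnote d, on the 2-week call | Not specified | Not specified | Not specified |

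The monitoring row has 17 cells for 17 columns. Only the first screening visit is blank, so the mark at the 2-week call is not a misalignment in the table. Footnote e is the only source that leaves AEs out of this call.

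**The case against.** The strongest reply has four parts.

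*AE assessment at the call is already planned.* Section 6.5 and the marked row with footnote y both require it, and the Schedule introduces itself as an overview that refers sites to the procedures sections. This stands. A reader might infer from footnote e that the plan does not collect non-serious AEs after treatment, or fails to cover its own safety window. The documents do not support that; they show one footnote at odds with the rest.

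*Footnote d does not restrict the call.* A reader might infer that it does, because the SAE wording follows closely on the mention of the 2-week call. That wording belongs to the additional telephone contacts, so this part stands too. Adding AEs to footnote d would do harm: it would extend non-serious AE questioning well past the 14 days of Section 8.1, and would clash with Section 6.7, which keeps those contacts brief and focused.

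*The call is not everyone's last contact.* This stands for early stoppers who agree to follow-up. It would be wrong to infer that they are the worst covered for all events. For SAEs and cardiovascular events they are better covered than completers; only for non-serious AEs is the gap not reached by later telephone contacts.

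*A symmetric tolerance is ordinary, the windows are only recommended, and the recording duties do not depend on the call.* This stands in part. A later recommended window would not forbid an early call, and related SAEs are reportable at any time. But nothing in the plan makes Day 14 the earliest recommended date. The any-time rule covers only SAEs judged related that reach the investigator, so unrelated SAEs in completers, and non-serious AEs, still depend on being volunteered.

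**Conclusion.** The point holds as a minor inconsistency with an inexpensive remedy. The recommended call window opens 3 days before the recording period closes, so up to 3 of 14 days (21%) can pass without a scheduled contact for subjects completing Week 104. For early stoppers in follow-up, the same days lack a scheduled telephone enquiry about non-serious AEs only. Separately, footnote e contradicts Section 6.5 and footnote y on the content of the call.

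The size is small: at most 3 days per subject for an in-window call, or about 0.86 day on average if calls are spread evenly over Days 11 to 17, which is an assumption. The documents give no event rate for these days, so the loss can be stated in days but not in events. The Week 26 efficacy analysis is unaffected.

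A reader might go further and conclude that post-treatment safety is not ascertained. That does not follow. AE assessment at the call is scheduled, volunteered events within 14 days must still be recorded, and cardiovascular collection continues after drug is stopped.

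**What to change.** 1. In the Schedule's window row, footnotes b and e, and Section 6.5, change the recommended call window to 14 days plus up to 3 days (Day 14 to Day 17). The maximum number of days left after an in-window call then falls from 3 to 0.
2. In footnote e, state that the call assesses AEs as well as SAEs, in line with Sections 6.5 and 8.1 and footnote y.
3. Leave footnote d unchanged.

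The cost is wording only, with the same single telephone call. Some calls will come a few days later than they otherwise would. Because the windows remain recommended, an early call is still possible, but it would no longer be in-window.

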Appendix 1. Collection and Management of Specimens for Future Biomedical
Research..... 115

Appendix 2. Biomarker Brochure..... 121

090177e1848ce2dd\Approved\Approved On: 23-Sep-2013 15:48

LIST OF ABBREVIATIONS

| Abbreviation | Term |
|------------------|--|
| β -hCG | beta human chorionic gonadotropin |
| ACE | angiotensin-converting enzyme |
| ADR | adverse drug reaction |
| AE | adverse event |
| AHA | anti-hyperglycemic agent |
| ALT | alanine transaminase |
| ANCOVA | analysis of covariance |
| Apo A1 | apolipoprotein A1 |
| ApoB | apolipoprotein B |
| AST | aspartate transaminase |
| AUC | area under the concentration-time curve |
| BMD | bone mineral density |
| BMI | body mass index |
| BP | blood pressure |
| BPM | beats per minute |
| BUN | blood urea nitrogen |
| CHF | Congestive heart failure |
| C _{max} | maximum observed measurable concentration |
| CRA | clinical research associate |
| CRF | case report form |
| CSA | clinical study agreement |
| CTX | carboxy-terminal cross-linking telopeptides of Type I collagen |
| CV | cardiovascular |
| DNA | deoxyribonucleic acid |
| DPP-4 | dipeptidyl peptidase-4 |
| DXA | dual energy X-Ray Absorptiometry |
| ECG | electrocardiogram |
| ECI | event of clinical interest |

090177e1848ce2dd\Approved\Approved On: 23-Sep-2013 15:48

| | |
|------------------|---|
| ED ₅₀ | dose achieving 50% of maximum response |
| EEA | European Economic Area |
| eGFR | estimated glomerular filtration rate |
| EMA | European Medicines Agency |
| ER | Extended Release |
| ET | early termination of the study |
| FAC | Fracture Adjudication Committee |
| FDA | Food and Drug Administration |
| FBR | Future Biomedical Research |
| FFSG | fasting fingerstick glucose |
| FPG | fasting plasma glucose |
| GCP | Good Clinical Practice |
| HA | hypoglycemia assessment |
| HbA1C | glycated/glycosylated hemoglobin |
| HDL-C | high density lipoprotein cholesterol |
| HR | heart rate |
| ICH | International Conference on Harmonisation |
| IEC | independent ethics committee |
| IND | investigational new drug application |
| iPTH | intact parathyroid hormone |
| IR | Immediate Release |
| IRB | institutional review board |
| IUD | Intra-uterine device |
| IVRS | interactive voice response system |
| LDL-C | low density lipoprotein cholesterol |
| LMP | last menstruation period |
| MACE | major adverse cardiovascular events |
| MDRD | Modification of Diet in Renal Disease |
| N/A | Not applicable |
| NASH | Non-alcoholic steatohepatitis |
| NOAEL | no observed adverse effect level |

090177e1848ce2dd\Approved\Approved On: 23-Sep-2013 15:48

| | |
|-------------|--|
| NPH | Neutral protamine Hagedorn |
| NYHA | New York Heart Association |
| P1NP | procollagen type I N-terminal propeptide |
| PK | pharmacokinetic(s) |
| PR interval | time from the beginning of the P wave to the end of the QRS complex on electrocardiogram |
| PTH | parathyroid hormone |
| QD | once daily |
| QRS | the deflections in an electrocardiographic tracing and represent ventricular activity of the heart |
| QT | time from the beginning of the QRS complex to the end of the T wave on electrocardiogram |
| QTcB | corrected QT interval Bazett's formula |
| QTcF | corrected QT interval Fridericia's formula |
| RNA | ribonucleic acid |
| S1 | Screening Visit 1 |
| S2 | Screening Visit 2 |
| S3 | Screening Visit 3 |
| S2/S3 | combined Screening Visits 2 and 3 |
| SAE | serious adverse event |
| SAP | statistical analysis plan |
| SD | standard deviation |
| SERM | Selective Estrogen Receptor Modulators |
| SGLT1 | Sodium Glucose co-Transporter 1 |
| SGLT2 | Sodium Glucose co-Transporter 2 |
| SLC5A | Sodium Glucose co-Transporter gene family |
| SOA | schedule of activity |
| SRSD | single reference safety document |
| SUSAR | suspected unexpected serious adverse reactions |
| T2DM | type 2 diabetes mellitus |
| TIA | Transient ischemic attack |
| TSH | thyroid-stimulating hormone |

090177e1848ce2dd\Approved\Approved On: 23-Sep-2013 15:48

Ertugliflozin (MK-8835/PF-04971729)

MK-8835-007-00/B1521017

Final Protocol, 20 September 2013

| | |
|-----|---------------------------|
| UGE | urinary glucose excretion |
| US | United States |
| UTI | urinary tract infections |

090177e1848ce2dd\Approved\Approved On: 23-Sep-2013 15:48

1. INTRODUCTION

1.1. Indication

Use in patients with type 2 diabetes mellitus (T2DM) to improve glycemic control with once daily dosing with the Sodium Glucose co Transporter 2 (SGLT2) inhibitor ertugliflozin.

1.2. Background

There has been an increase in the global prevalence of T2DM largely attributed to rising rates of excess body weight and obesity. In 2011, diabetes was estimated to affect more than 365 million people worldwide between the ages of 20-79 years and the prevalence of diabetes is projected to reach more than 550 million by the year 2030.¹ T2DM also represents one of the largest medical burdens in the United States resulting in direct medical costs of \$176 billion and \$69 billion in loss of productivity in 2012.² At present, it is estimated that 25.8 million people in the US have diabetes (8.3% of the population) of which 7 million remain undiagnosed.³ T2DM accounts for approximately 90-95% of all cases of diabetes. Approximately 85% of patients with T2DM are obese or overweight, a key factor underlying the development and maintenance of insulin resistance.^{4,5} Individuals with T2DM have an increased risk of developing both microvascular and macrovascular disease-associated complications, including nephropathy, neuropathy, retinopathy, and cardiovascular disease, and are 2 to 4 times more likely to die from cardiovascular disease than adults who do not have diabetes.⁶ Orally administered pharmacological agents that lower glucose while also reducing other risk factors, eg, by lowering body weight and reducing blood pressure, represent a major advantage in the treatment of diabetes.

The sodium glucose co-transporter family (SLC5A) consists of 12 known members, including 6 gene products named SGLTs.⁷ SGLT1, a low capacity, high-affinity transporter with a sodium: glucose stoichiometry of 2:1 transports D-glucose as well as D-galactose and is primarily distributed in the intestine; it is also found in the S3 segment of the proximal tubule of the kidney where it is responsible for approximately 10% of glucose reabsorption. In contrast, SGLT2 is primarily located in the S1/S2 segments of the proximal tubule of the kidney and is responsible for the reabsorption of approximately 90% of the glucose from the urine. SGLT2 utilizes a sodium ion gradient to actively transport glucose in a 1:1 stoichiometry and has been characterized as a high capacity, low affinity glucose transporter.^{8,9,10}

Ertugliflozin (MK-8835/PF-04971729) is a potent inhibitor of the Sodium-Glucose co-transporter type 2 (SGLT2) and possesses a high selectivity over glucose transport via Sodium-Glucose co-Transporter 1 (SGLT1) and several other glucose transporters (GLUT1-4). Ertugliflozin inhibits renal glucose reabsorption resulting in urinary glucose excretion and thereby reducing plasma glucose and HbA1c in subjects with T2DM. Ertugliflozin is being developed as an adjunct to diet and exercise to improve glycemic control in patients with T2DM.

The purpose of this trial is to evaluate the efficacy and safety of the addition of ertugliflozin to the treatment of subjects with T2DM and inadequate glycemic control on metformin

monotherapy. Metformin is the standard and preferred first line pharmacological agent for T2DM. However, due to the progressive nature of T2DM, many subjects may have poor glycemic control despite metformin monotherapy. Since ertugliflozin improves glycemic control via a mechanism independent of insulin, it could potentially represent a valuable therapy across the typical disease progression of T2DM, including individuals with inadequate glycemic control on metformin monotherapy.

In addition, this study will assess changes in bone mineral density (BMD) by dual-energy X-ray absorptiometry (DXA), and so provide important information on the bone safety of ertugliflozin.

